9.3 Direct cost parameters

Direct costs will be assessed based on concomitant medications, concurrent medical procedures, health care provider consultations not foreseen by protocol, hospital stays, and ER visits.

All direct cost parameters will be summarized for the SS.

All direct cost parameters will be listed.

9.3.1 Concomitant medications

The analysis of concomitant medications is described in Section 6.4.7 and Section 6.4.8.

9.3.2 Concurrent medical procedures

The number of concurrent medical procedures per subject will be summarized by 6-month time intervals for the corresponding 6-month Exposure Duration Cohorts. Additionally, the number of concurrent medical procedures will be summarized for subjects with < 6 months of exposure to BRV. The number of concurrent medical procedures per subject will be summarized using the categories 0, 1, 2, 3, 4, and 5 or more. Summaries will be provided for the SS.

Medical procedures are defined to be concurrent, if they start after first dose of BRV and will be attributed to 6-month time intervals based on the date of the procedure. For subjects with < 6 months of exposure to BRV, all medical procedures on or after the first dose of BRV will be counted.

9.3.3 Additional healthcare provider consultations

The number of additional healthcare provider visits per subject will be summarized by 6-month time intervals for the corresponding 6-month Exposure Duration Cohorts. Additionally, the number of additional healthcare provider visits will be summarized for subjects with < 6 months of exposure to BRV. The number of additional healthcare provider visits will be summarized using the categories 0, 1, 2, 3, 4, and 5 or more. Summaries will be provided for the SS.

Additional healthcare provider visits will be attributed to 6-month time intervals based on the date of the procedure. For subjects with < 6 months of exposure to BRV, all additional healthcare provider visits on or after the first dose of BRV will be counted.

The number of additional healthcare provider visits will be summarized by type of provider (General Practitioner, Specialist Physician, Nurse, or Other) and by 6-month time intervals for the corresponding 6-month Exposure Duration Cohorts, and for subjects with < 6 months of exposure to BRV. Percentages will be relative to the total number of health care provider visits within each 6-month time interval (for summaries by exposure duration cohorts) or the total number of healthcare provider visits for subjects with < 6 months of exposure to BRV. As above, this summary will be provided for the SS.

9.3.4 Hospital stays

The number of hospital stays per subject will be summarized by 6-month time intervals for the corresponding 6-Month Exposure Duration Cohorts. Additionally, the number of hospital stays will be summarized for subjects with < 6 months of exposure to BRV. The number of hospital stays will be summarized using the categories 0, 1, 2, 3, 4, and 5 or more. Summaries will be provided for the SS.

Hospital stays will be attributed to 6-month time intervals based on the date of the admission. For subjects with < 6 months of exposure to BRV, all hospital stays on or after the first dose of BRV will be counted.

The number and percentage of subjects with specified categories of duration of hospital stays will be summarized by 6-month time intervals and the 6-Month Exposure Duration Cohorts. Additionally, the number and percentage of specified categories of hospital stays will be summarized for subjects with < 6 months of exposure to BRV. Duration of hospital stays will be summarized descriptively for the SS.

The number and percentage of subjects with hospitals stays by duration categories as defined in Section 3.104.4 will be summarized by 6-month time intervals for the corresponding 6-Month Exposure Duration Cohorts. Additionally, this table will be produced for subjects with < 6 months of exposure to BRV.

9.3.5 Emergency room visits

The number of ER visits per subject will be summarized by 6-month time intervals for the corresponding 6-month Exposure Duration Cohorts, and for subjects with < 6 months of exposure to BRV. The number of ER visits per subject will be summarized using the categories 0, 1, 2, 3, 4, and 5 or more. Summaries will be provided for the SS.

ER visits will be attributed to 6-month time intervals based on the date of the ER visit. For subjects with < 6 months of exposure to BRV, all ER visits on or after the first dose of BRV will be counted.

9.4 Achenbach Child Behavior Checklist

The Achenbach CBCL is completed at the ScrV (DE subjects only), FEV, YEV, FV, and at the EDV in the case of early discontinuation. For LTFU subjects (except for those from core studies EP0065 and N01349), at the EV, the Achenbach CBCL score is obtained from the Baseline of the core study and should not be recorded in the eCRF for N01266. For DE subjects, the Achenbach CBCL completed at the ScrV and for EP0065 LTFU subjects the Achenbach CBCL completed at the EV, will be the Baseline assessment. For LTFU subjects from core study N01349 Achenbach CBCL Baseline assessment is not available, as this questionnaire was not performed in core study N01349 and not recorded at EV in N01266 study.

Calculated T-score values and raw score values and the corresponding change from Baseline for each CBCL/1½-5 syndrome (aggressive behavior, anxious / depressed, attention problems, emotionally reactive, sleep problems, somatic complaints, withdrawn) will be summarized for each scheduled visit during the Evaluation Period if available.

Calculated T-score and raw score values and corresponding change from Baseline for each CBCL/6-18 syndrome (aggressive behavior, anxious / depressed, attention problems, rule-breaking behavior, social problems, somatic complaints, thought problems, and withdrawn / depressed) will be summarized for each scheduled visit during the Evaluation Period if available.

Additionally, for all CBCL/1½-5 syndromes as well as CBCL/6-18 syndromes, shift tables for T-scores will be done. These shift tables are based on T-score legacy categorization “Normal”, “Borderline” or “Clinical Significant” and the dichotomous approach “Normal” or “Borderline or Clinical Range” as described in Section 3.10.5.1 and will summarize the shift from Baseline for each visit during the Evaluation Period if available and for the last assessment. These shift tables will not include LTFU subjects from core studies N01349 as Baseline values are not available from this study.

All Achenbach CBCL data will be listed. Data assessed on unscheduled visits will be included in listings only.

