3.2.6 Last Value on BRV treatment

The Last Value on BRV treatment for all assessments is the final available result obtained after the first dose of BRV and prior to or on the date of the final dose of BRV within evaluation period. All scheduled and UV assessments within evaluation period will be considered. Last Value will be determined separately for each vital sign, ECG and laboratory parameter.

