3.2.9 Mapping of assessments performed at Early Discontinuation Visit

Efficacy and safety assessments at an EDV that correspond to a scheduled visit will be summarized at the scheduled visit corresponding to the EDV if the assessment was scheduled to occur at that visit. Such assessments will also be considered for Last Value on BRV treatment (see Section [3.2.6](#)).

In particular, clinical laboratory parameters, vital signs, and body weight are assessed at all Evaluation Period visits, and so all assessments of these variables at EDVs corresponding to a scheduled visit will be mapped to the corresponding scheduled visit.

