9.5 BRIEF-P and BRIEF assessment

The BRIEF-P/BRIEF assessments are completed at the ScrV (DE subjects only), FEV, YEV, FV, and at the EDV in the case of early discontinuation. For LTFU subjects (except those coming from core studies N01349, EP0065 and N01263), at the EV of N01266, the BRIEF-P/BRIEF score will be obtained from Baseline of the core study and should not be recorded in the eCRF for N01266. For DE subjects and LTFU subjects from core study EP0065, the Baseline BRIEF-P/BRIEF should be completed at the ScrV. As BRIEF-P/BRIEF questionnaires have not been recorded in core studies N01263 and N01349 and as this data was not collected at EV of N01266, no Baseline values are available for those LTFU subjects within N01266.

The BRIEF-P or BRIEF appropriate for each subject's age should be completed, with the following exception: For subjects who completed the BRIEF-P at the Baseline assessment and

turn 5 years of age between that assessment and the initial YEV, the BRIEF-P should be completed through and including the initial YEV, and subsequently the BRIEF should be completed.

Calculated T-score and raw score values and corresponding change from Baseline (if available) for the 3 indexed scores (Inhibitory Self-Control, Flexibility and Emergent Metacognition) and the GEC for the BRIEF-P questionnaire will be summarized for each visit during the Evaluation Period where the questionnaire is entered.

Calculated T-score and raw score values and corresponding change from Baseline (if available) for the 2 indexed scores (Behavioral Regulation and Metacognition) and the GEC for the BRIEF questionnaire will be summarized for each visit during the Evaluation Period where the questionnaire is entered.

In addition, for all indexed scores and GEC for BRIEF as well as BRIEF-P questionnaire, shift tables for T-scores will be done. These shift tables are based on T-score legacy categorization “Normal”, “Borderline” or “Clinical Significant” and the dichotomous approach “Normal” or “Potentially Clinically Significant” as described in Section 3.10.5.2 and Section 3.10.5.3 respectively and will summarize the shift from Baseline for each visit during the Evaluation Period where the questionnaire is entered. These shift tables will not include LTFU subjects from core studies N01349 and N01263 as Baseline values are not available from these studies,

All BRIEF-P and BRIEF assessment data (including validity scores negativity and inconsistency) will be listed.

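### SAP 9.4 names no Early Discontinuation or Last Value row for the CBCL mean-change tables, so exit scores that fall at Minimal Evaluation Visit time points have no stated place in them

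*SAP*

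**What the plan says.** - **Collection (9.4).** "The Achenbach CBCL is completed at the ScrV (DE subjects only), FEV, YEV, FV, and at the EDV in the case of early discontinuation". Minimal Evaluation Visits (MEVs) are not in the list.
- **Mean tables (9.4).** T-scores, raw scores and change from Baseline for each syndrome "will be summarized for each scheduled visit during the Evaluation Period if available".
- **Shift tables (9.4).** These are planned "for each visit during the Evaluation Period if available and for the last assessment".
- **Other handling (9.4).** All CBCL data are listed. "Data assessed on unscheduled visits will be included in listings only".
- **Mapping of EDV results (3.2.9).** They "will be summarized at the scheduled visit corresponding to the EDV if the assessment was scheduled to occur at that visit". The section names laboratory parameters, vital signs and body weight as assessed at every Evaluation Period visit. The CBCL is not named.
- **Table labels (3.2.5).** The Month X label is for scheduled visits in the Evaluation Period. Final Visit, Early Discontinuation Visit and Last Value are separate labels.
- **Last Value (3.2.6).** "The Last Value on BRV treatment for all assessments is the final available result" obtained on treatment within the Evaluation Period.
- **Comparison (8.4.1).** The vital-signs tables name EDV, Last Value and Final Visit in addition to the Evaluation Period visits.

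**The concern.** Section 9.4 treats its two kinds of CBCL table differently. The shift tables include a last assessment, while the value and change tables stop at scheduled visits. Where the SAP wants EDV or Last Value rows elsewhere (8.3, 8.4.1), it names them.

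Change from Baseline in the CBCL is a listed variable (2.2.3) and serves a stated objective, the effect on behaviour (2.1.3). The study is descriptive with no model or test (3.1), so the tables are the result. Section 4.2 accepts that dropouts may influence long-term outcomes and offers selected summaries by exposure cohort, but 9.4 provides none for the CBCL. Without a last-assessment row there is no end-of-treatment mean change that includes the children who left. If those children tend to have worse behaviour scores, the by-visit means would look better than the whole treated group.

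**Working it through.** The SAP states no percentage on this point, so there is no figure to reproduce. The check asks how many EDV scores the mapping rule leaves without a row.

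**Inputs.** Table 2-1 gives MEVs at M1, M3, M9, M15, M21 and so on; FEVs at M2, M6, M18 and so on; and YEVs every 12 months. A month is 30 days (3.2.4). Visit tolerances are ±7 days up to M3 and ±15 days from M6, applied here around the nominal day. The timing of discontinuation is an assumption: uniform, or exponential at 20% or 40% per 360 days, over 1 to 8 years.

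**Share of scheduled post-entry visits that are MEVs.** 3/6 in year 1, 7/14 by year 3, 11/22 by year 5, which is 50% each time.

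**Year 1 with uniform timing, 360 days:**

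| How an EDV corresponds to a visit | EDV days without a row | Share |
|---|---|---|
| Nearest visit is an MEV | 45 (M1) + 60 (M3) + 90 (M9) = 195 | 195/360 = 54.2% |
| Next due visit is an MEV | 30 + 30 + 90 = 150 | 150/360 = 41.7% |
| Strict windows: no visit matched, or an MEV matched | 237 + 61 = 298 | 298/360 = 82.8% |

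For the strict case, MEV windows cover 15 + 15 + 31 = 61 days and FEV/YEV windows cover 15 + 31 + 16 = 62 days. That leaves 360 − 123 = 237 days matching no visit.

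**All horizons and timing assumptions:**
- nearest visit: 50.5% to 55.6%
- next due visit: 41.7% to 49.2%
- strict windows: about 83%
- EDV label in 3.2.5 read as giving the CBCL tables their own row: 0%

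**What the shift tables can and cannot show.** Under 3.10.5.1 any T-score below 65 is Normal. A child moving from 50 to 64 has worsened by 14 points and stays in the same cell under both categorisations. Only a mean-change table would show it.

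**After adding the row.** No exit score with a usable Baseline on the same form is left out (0%). Subjects from N01349 have no Baseline CBCL (9.4), so they have no change score under any version of the table.

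**The case against.** The omission is inferred from silence. The EDV closes the Evaluation Period (3.2.3) and has its own table label (3.2.5), and 3.10.5.1 calculates CBCL change at each visit of that period. Only unscheduled-visit data are confined to listings, so the word scheduled in 9.4 might merely mean not unscheduled. This reading is possible and would bring the loss to nil. It is the less natural one, because the wording matches the Month X label and 8.4.1 names the EDV separately even after the Evaluation Period visits. That both readings are open is itself a reason to settle the text.

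Three further objections stand and limit the point.

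- **The exit scores are not lost.** They are listed and, with a Baseline, they enter the last-assessment shift tables for every syndrome. Adverse events leading to discontinuation also have their own tables (8.2.2).
- **Section 3.2.6 defines a term.** It does not require a Last Value row in questionnaire tables, and it goes on to mention only vital signs, ECG and laboratory parameters.
- **The other questionnaires differ.** A reader might infer the same gap in 9.5 to 9.7. The documents do not support that. The BRIEF-P/BRIEF shift tables "will summarize the shift from Baseline for each visit during the Evaluation Period where the questionnaire is entered", 9.7 uses similar wording for the PedsQL, and 9.6 refers to each visit. None of these is limited to scheduled visits, so the EDV is not excluded.

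A reader might also want to put a size on the bias. With an assumed 40% leaving and exit scores 5 points worse, a pooled end-of-treatment mean would be 0.4 × 5 = 2.0 with all exit scores, and 0.5 × 0.4 × 5 / (1 − 0.5 × 0.4) = 1.25 with half dropped. All the inputs are assumed and 9.4 plans no pooled mean, so this is not an estimate of any planned result.

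**Conclusion.** The point holds for the CBCL value and change tables in 9.4. On the most natural reading, EDV scores at MEV time points have no row there, because mapping under 3.2.9 applies only "if the assessment was scheduled to occur at that visit".

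The size depends on a window that the SAP does not set: about 42% to 56% of EDV scores under nearest-visit or next-visit assignment, about 83% under strict windows, and none if an EDV row is implied. A flat statement that half of the exit scores are omitted would go further than the text. So would a claim that the tables are biased towards no harm, since nothing in the SAP shows that leavers score worse. Understatement of worsening is conditional on that assumption.

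This is an inexpensive improvement to a descriptive summary of a non-primary variable. It does not affect the primary safety analysis.

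**What to change.** - In 9.4, add a Last Value on BRV treatment row to the CBCL T-score, raw-score and change-from-Baseline tables, matching the last assessment in the CBCL shift tables.
- State that this row takes in every EDV CBCL score, whether or not the EDV maps to a scheduled visit. This needs saying because 3.2.9 carries into Last Value only EDV results that correspond to a scheduled visit. Section 3.2.6 also stops at the final dose within the Evaluation Period, so say how an EDV held after that dose is treated.
- Optionally add an EDV row, which would show the leavers' scores on their own.
- In 3.2.9, define when an EDV corresponds to a scheduled visit.
- A Last Value row in 9.5 to 9.7 is optional, for consistency only. It does not correct an omission.

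The cost is a few sentences of SAP text and one or two rows per table. The data are already collected.

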9.5 BRIEF-P and BRIEF assessment

The BRIEF-P/BRIEF assessments are completed at the ScrV (DE subjects only), FEV, YEV, FV, and at the EDV in the case of early discontinuation. For LTFU subjects (except those coming from core studies N01349, EP0065 and N01263), at the EV of N01266, the BRIEF-P/BRIEF score will be obtained from Baseline of the core study and should not be recorded in the eCRF for N01266. For DE subjects and LTFU subjects from core study EP0065, the Baseline BRIEF-P/BRIEF should be completed at the ScrV. As BRIEF-P/BRIEF questionnaires have not been recorded in core studies N01263 and N01349 and as this data was not collected at EV of N01266, no Baseline values are available for those LTFU subjects within N01266.

The BRIEF-P or BRIEF appropriate for each subject's age should be completed, with the following exception: For subjects who completed the BRIEF-P at the Baseline assessment and

turn 5 years of age between that assessment and the initial YEV, the BRIEF-P should be completed through and including the initial YEV, and subsequently the BRIEF should be completed.

Calculated T-score and raw score values and corresponding change from Baseline (if available) for the 3 indexed scores (Inhibitory Self-Control, Flexibility and Emergent Metacognition) and the GEC for the BRIEF-P questionnaire will be summarized for each visit during the Evaluation Period where the questionnaire is entered.

Calculated T-score and raw score values and corresponding change from Baseline (if available) for the 2 indexed scores (Behavioral Regulation and Metacognition) and the GEC for the BRIEF questionnaire will be summarized for each visit during the Evaluation Period where the questionnaire is entered.

In addition, for all indexed scores and GEC for BRIEF as well as BRIEF-P questionnaire, shift tables for T-scores will be done. These shift tables are based on T-score legacy categorization “Normal”, “Borderline” or “Clinical Significant” and the dichotomous approach “Normal” or “Potentially Clinically Significant” as described in Section 3.10.5.2 and Section 3.10.5.3 respectively and will summarize the shift from Baseline for each visit during the Evaluation Period where the questionnaire is entered. These shift tables will not include LTFU subjects from core studies N01349 and N01263 as Baseline values are not available from these studies,

All BRIEF-P and BRIEF assessment data (including validity scores negativity and inconsistency) will be listed.

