BRV (tablet and oral solution) should be administered twice daily (bid) in 2 equally divided doses. All LTFU subjects must be able to tolerate the minimum dose specified in the core study to be eligible for entry into the Evaluation Period of N01266. All DE subjects must be able to tolerate at least 1mg/kg/day during the Up-Titration Period prior to entering the Evaluation Period of N01266.

The maximum allowable BRV dose is 5.0mg/kg/day (2.5mg/kg bid), not to exceed a dose of 200mg/day. Subjects will receive oral solution or tablets, as appropriate. With the exception of dose adjustments for BRV during the Up-Titration Period, which should be made in accordance with the protocol-specified guidelines, dose adjustments of BRV and any concomitant antiepileptic drugs (AEDs) are allowed at any time based on clinical judgment.

Subjects will receive BRV treatment in this study for at least 3 years, until approval of BRV has been obtained for pediatric subjects in their age range, until a managed access program is established as allowed per country-specific requirements in addition to legal and regulatory guidelines, until subjects transition to another BRV study, or until the investigational product development in the related age range of the pediatric population is stopped by the Sponsor, whichever comes first.

For LTFU subjects, the EV is the first study visit. For DE subjects, the EV occurs after subjects have completed the ScrV and at least 1 Titration Visit (TV), and have maintained acceptable tolerability and seizure control on the same daily dose of BRV (no lower than the minimum specified dose) for 7 ± 2 days of the Up-Titration Period. For subjects who continue in this study until it ends, the Evaluation Period will extend from the EV until the final evaluation visit (Final Visit, FV). For subjects who prematurely discontinue the study, the Evaluation Period will last from the EV until the Early Discontinuation Visit (EDV), followed by a maximum 4-week Down-Titration Period, a 2-week Safety (Drug-Free) Period, and a final Safety Visit (SV). Subjects already enrolled in N01266 may participate in EP0065 (an intravenous [iv] BRV study for pediatric subjects), if eligible, and then resume participation in N01266.

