3.2.3 Study periods

[Table 3–1](#) shows which study periods are applicable to DE and LTFU subjects:

This document cannot be used to support any marketing authorization application and any extensions or variations thereof.
PUBLIC COPY

Table 3-1: Study periods

Period		Screening Period	Up-Titration Period			Evaluation Period							Down-Titration Period	Safety Period		
Subjects	Visit	ScrV	TV1	TV2	TV2	EV	MEV	FEV	MEV	FEV	MEV	YEV	...	FV/EDV	DTV	SV
			V1	V2	V3	V4	V5	V6	V7	...						
Subjects	DE	x	x	x	x	x	x	x	x	x	x	x	x	x	(x)	(x)
	LTFU					x	x	x	x	x	x	x	x	x	(x)	(x)
	Early Discontinuations												x	x	x	x

(x) – only applicable if the subject does not switch to another BRV study or is taking marketed drug after FV

The study is divided into 5 periods: Screening Period, Up-Titration Period, Evaluation Period, Down-Titration Period, and the Safety Period.

There is a Screening Period for all DE subjects. For DE subjects, this comprises assessments performed prior to the first dose of BRV in N01266. So start date of Screening Period is date of written informed consent and end date is the day before first dose of BRV (TV1-1). Although, patients in LTFU studies will not attend a screening visit, the screening information comprises information collected at various assessments during the core study and consequently will have been collected at different times depending on the domain. Domain specific information is detailed in Section 3.3.

The Up-Titration Period is only applicable to DE subjects, and the start date is the date of the first dose of BRV. The following algorithm is used to determine the end date:

- If the subject enters the Evaluation Period, the date 1 day prior to the EV is the end date
- If the subject does not enter Evaluation Period, the Up-Titration Period ends on the date of the final dose of BRV

For the Evaluation Period, the start date is the date of the first dose of BRV on or after the EV date, and the following algorithm is used to determine the end date:

- If the subject continues the study until it ends, the Evaluation Period ends on the date of FV
- If the subject prematurely discontinues the study, the date of EDV is the end date

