3.3 Definition of Baseline values

Baseline for all study outcomes will be determined using different methods depending on whether the subject is LTFU or DE.

Unless otherwise specified, Baseline values will be determined as follows:

- DE subjects: the last (most recent) available pre-dose measurement of the corresponding outcome will be used as Baseline
- LTFU subjects:
 - if available, Baseline values from the previous BRV core studies will be used as Baseline
 - otherwise the last (most recent) available measurement assessed between day of final on-treatment measurement in core study and the day before first BRV administration in N01266 will be used as Baseline

For laboratory parameters, vital signs (systolic blood pressure [SBP], diastolic blood pressure [DBP], and pulse rate), body weight, and ECGs, Baseline values will be determined as follows:

- DE subjects: the last (most recent) available pre-dose measurement of the corresponding outcome will be used as Baseline
- LTFU subjects: the last (most recent) available scheduled or UV assessment up to the day of subjects first BRV administration in core study will be used as Baseline (most recent measurement up to first BRV administration in core study, not in N01266 as in the general definition of Baseline values)

Baseline will be determined separately for each individual clinical laboratory parameter for hematology, biochemistry, endocrinology and urinalysis assessments.

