- If T-score is >= 65 then CS category = "Clinically Significant".

T-scores will also be categorized using the dichotomous approach with regard to CS to summarize categorical shift from Baseline. The categories for CS are defined as follows:

- If T-score is < 65 then CS category = "Normal"
- If T-score is >= 65 then CS category = "Potentially Clinically Significant".

Two validity scales will also be derived: Negativity to assess the extent to which the respondent answers selected BRIEF items in an unusually negative manner and Inconsistency to assess the extent to which the respondent answers similar BRIEF items in an inconsistent manner. The Negativity scale is the number of items in 8, 13, 23, 30, 62, 71, 80, 83 and 85 with a score of 3, and so has a range of 0 to 9. A score of 4 or less is considered acceptable, 5 to 6 elevated and 7 or more highly elevated.

For the Inconsistency scale, there are 10 item pairs of related questions. The Inconsistency scale is the sum of the absolute values of the difference in scores for the items in each item pair, and so ranges from 0 to 20. The item pairs are questions 7 and 25, 11 and 22, 27 and 17, 33 and 32, 38 and 59, 41 and 65, 42 and 63, 44 and 54, 53 and 60, and 55 and 44. A score of 6 or less is acceptable, 7 or 8 questionable and 9 or more inconsistent.

BRIEF will be conducted at ScrV, EV (for DE and LTFU subjects respectively), at FEVs, YEVs and FV/EDV.

Change from Baseline in BRIEF scores (for raw scores and T-scores) will be calculated as:

Change from Baseline in BRIEF

= BRIEF score at postBaseline visit – BRIEF score at Baseline

at each visit in the Evaluation Period, if Baseline value is available. A change from Baseline < 0 indicates improvement and a change from Baseline > 0 worsening.

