Two validity scales will also be derived: Negativity to assess the extent to which the respondent answers selected BRIEF-P items in an unusually negative manner and Inconsistency to assess the extent to which the respondent answers similar BRIEF-P items in an inconsistent manner. The Negativity scale is the number of items in 30, 44, 46, 47, 53, 55, 56, 57, 59 and 63 with a score of 3, and so has a range of 0 to 10. A score of 2 or less is considered acceptable, 3 as elevated and 4 or more highly elevated.

For the Inconsistency scale, there are 10 item pairs of related questions. The Inconsistency scale is the sum of the absolute values of the difference in scores for the items in each item pair, and so ranges from 0 to 20. The item pairs are questions 1 and 11, 3 and 33, 5 and 45, 10 and 20, 11 and 26, 16 and 21, 18 and 52, 33 and 38, 43 and 52, and 48 and 54. A score of 7 or less is acceptable and 8 or more inconsistent.

BRIEF-P will be conducted at ScrV, EV (for DE and LTFU subjects respectively), at FEVs, YEVs and FV/EDV.

Change from Baseline in BRIEF-P scores (raw scores and T-scores) will be calculated as:

$$\begin{aligned} \text{Change from Baseline in BRIEF - P} \\ = \text{BRIEF - P score at postBaseline visit} - \text{BRIEF - P score at Baseline} \end{aligned}$$

at each visit in the Evaluation Period, if Baseline value is available for all BRIEF-P scores (the 5 scales, 3 Indices and GEC scores). A change from Baseline < 0 indicates improvement and a change from Baseline > 0 worsening.

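### Section 9.5 ties the BRIEF-P/BRIEF Baseline of EP0065 roll-overs to a Screening Visit that LTFU subjects do not attend; the rest of the SAP points to the Entry Visit

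*SAP*

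**What the plan says.** Section 9.5 sets the rule: "For DE subjects and LTFU subjects from core study EP0065, the Baseline BRIEF-P/BRIEF should be completed at the ScrV". The same section opens by restricting that visit: "The BRIEF-P/BRIEF assessments are completed at the ScrV (DE subjects only), FEV, YEV, FV". It says that no BRIEF-P/BRIEF Baseline exists for roll-overs from N01263 and N01349, and it removes only those two groups from the shift tables. EP0065 is not among them.

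On visits, Section 3.2.3 says that "patients in LTFU studies will not attend a screening visit", and Section 2 says: "For LTFU subjects, the EV is the first study visit".

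The derivation sections give a different schedule. Section 3.10.5.2 reads: "BRIEF will be conducted at ScrV, EV (for DE and LTFU subjects respectively), at FEVs, YEVs and FV/EDV". Section 3.10.5.3 reads: "BRIEF-P will be conducted at ScrV, EV (for DE and LTFU subjects respectively), at FEVs, YEVs and FV/EDV".

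Section 3.3 holds the general Baseline rule, introduced by "Unless otherwise specified, Baseline values will be determined as follows". For LTFU subjects without a core-study Baseline, the window closes early: the latest measurement up to "the day before first BRV administration in N01266 will be used as Baseline".

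**The concern.** This sentence is an operative rule, because it decides which record becomes the Baseline. A programmer who follows it would look for a Screening Visit questionnaire for EP0065 roll-overs and would normally find none. Sections 3.10.5.2 and 3.10.5.3 calculate change only where a Baseline exists, so the result would be missing change and shift values with no flag. A second programmer, working from Sections 3.10.5.2 and 3.10.5.3, would take the Entry Visit record and produce different tables.

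The outcome at stake is cognition measured by BRIEF-P/BRIEF, one of the other objectives in Section 2.1.3. Section 9.5 evidently expects EP0065 subjects to contribute, since it leaves them in the shift tables.

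**Working it through.** The SAP states no figure to reproduce here. The check sets the rules side by side and then tests the Section 3.3 window by counting days.

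**Step 1. Which visit holds the Baseline for an EP0065 roll-over?**

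| SAP section | Instrument | Visit for EP0065 or LTFU subjects |
|---|---|---|
| 9.5, Baseline rule | BRIEF-P/BRIEF | Screening Visit (EP0065 named) |
| 9.5, opening sentence | BRIEF-P/BRIEF | Screening Visit for directly enrolled subjects only |
| 3.10.5.2 | BRIEF | Entry Visit (LTFU) |
| 3.10.5.3 | BRIEF-P | Entry Visit (LTFU) |
| 9.4 | CBCL | Entry Visit (EP0065 named) |
| 9.6 | Bayley-III | Entry Visit of N01266 (EP0065 named) |
| 9.7 | PedsQL | Entry Visit of N01266 (EP0065 named) |
| 2 and 3.2.3 | any | No Screening Visit; the Entry Visit comes first |

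Of the four questionnaire sections (9.4 to 9.7), only 9.5 points EP0065 subjects to the Screening Visit.

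**Step 2. Does the Section 3.3 default recover an Entry Visit value?** Its first limb uses the core-study Baseline. Section 9.5 lists EP0065 among the exceptions to taking the score from the core study, so that limb appears closed. The SAP implies, but does not state, that EP0065 recorded no BRIEF.

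The second limb is a window. Its inputs are:

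- Entry Visit = day 0.
- Window start = day of the final on-treatment core-study measurement. Take this as day 0, because the footnote to Table 2-1 equates the LTFU Entry Visit with the last evaluation visit of the core study.
- First N01266 dose = day d, with d ≥ 0, because Section 3.2.3 allows the first Evaluation Period dose on the Entry Visit date or later.
- Window end = d − 1.

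An Entry Visit questionnaire (day 0) is inside the window only if 0 ≤ d − 1, that is, d ≥ 1.

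| First dose day d | Window | Entry Visit questionnaire |
|---|---|---|
| 0 | 0 to −1 (empty) | excluded |
| 1 | 0 to 0 | included |
| 2 | 0 to 1 | included; used unless a later pre-dose value exists |

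The condition d ≥ 1 does not depend on the assumed start day, provided that the window opens on or before day 0. The default therefore fails exactly when dosing in N01266 starts on the Entry Visit date. The SAP permits this but does not say how often it happens.

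**Step 3. Is the default the governing rule?** Section 3.3 yields to any more specific rule. Sections 9.4 and 9.7 name the Entry Visit for EP0065 subjects and so displace it for CBCL and PedsQL. Section 9.5 also tries to be specific, but names a visit that these subjects do not have.

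**The case against.** A reader might infer more than the SAP supports: that every EP0065 roll-over ends up without a BRIEF Baseline. Four points stand against that.

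- Sections 3.10.5.2 and 3.10.5.3 plan an Entry Visit assessment for LTFU subjects, which a programmer could reasonably use. Section 9.5 treats EP0065 subjects as having a Baseline. The conflict is over the name of the visit; the SAP has not decided to do without the data.
- The Section 3.3 window is a default and excludes the Entry Visit value only with same-day dosing. Naming the right visit in Section 9.5 would displace it, as already happens for CBCL and PedsQL.
- Section 3.2.2 says that children who went from N01266 to EP0065 and back keep their original N01266 screening data. Any of them first enrolled directly would have a Screening Visit record. The SAP does not say whether such children count as EP0065 LTFU subjects.
- The term for the Screening Visit is used loosely elsewhere. Section 3.10.3 assigns seizure categories at that visit to subjects who include roll-overs.

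It is also tempting to say that the error makes the cognition, behavior and quality-of-life tables describe different populations. They already differ by design. Roll-overs from N01263 have no Baseline for BRIEF or PedsQL but are not excluded from the CBCL shift tables, and the minimum age is 18 months for CBCL against 2 years for BRIEF-P and PedsQL. Correcting Section 9.5 would not align them.

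These points limit the consequence. The contradiction within Section 9.5, and between it and the other sections, remains.

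**Conclusion.** The finding holds as an internal contradiction in a stated Baseline rule. Read literally, EP0065 roll-overs without an original N01266 screening record may lose their BRIEF-P/BRIEF change and shift values, against the evident intent of Section 9.5. The Section 3.3 default would not rescue an Entry Visit questionnaire completed on the day of the first N01266 dose.

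The size cannot be stated. The SAP gives neither the number of EP0065 roll-overs nor the share who started dosing on the Entry Visit date, so a total loss is not supported. The conclusion assumes that EP0065 supplied no usable BRIEF Baseline, which Section 9.5 implies, and that the questionnaire was completed at the Entry Visit, as Sections 3.10.5.2 and 3.10.5.3 schedule. The outcome is exploratory and summarized without testing, and the primary safety variables are untouched. It is a minor point that is worth correcting because the correction is nearly free.

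**What to change.** In Section 9.5, say that the Baseline BRIEF-P/BRIEF is completed at the Screening Visit for directly enrolled subjects and at the Entry Visit of N01266 for EP0065 LTFU subjects. Add that this Entry Visit assessment serves as Baseline even if the first N01266 dose is taken the same day, and that this overrides the Section 3.3 default for this outcome.

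The Section 3.3 window itself need not change. Widening it would alter the default Baseline for every outcome that relies on it, in order to repair one sentence.

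The cost is a wording edit confined to Section 9.5, with no new data collection and no change to the planned tables.
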